6.5.6. Desirability of Outcome Ranking (DOOR) at D5V or D11V

DOOR at D5V is defined by ranking all subjects (pooling together both treatment arms) according to OCO at D5V (lower is better) and using the number of days of antibiotic use at D5V (lower is better) as a tie-breaker for comparing the ranking of two subjects with the same OCO. DOOR at D11V is defined by ranking all subjects (pooling together both treatment arms) according to OCO at D11V (lower is better) and using the number of days of antibiotic use at D11V (lower is better) as a tie-breaker for comparing the ranking of two subjects with the same OCO. DOOR at D5V or at D11V is missing only if OCO or number of days of antibiotic use is missing for the respective visit.

The ranking algorithm for DOOR is implemented as follows. A score variable is created that adds the number of days of antibiotic use (as defined in Section 6.5.5) divided by 100 to the OCO. Subjects are then ranked

(DOOR) by the score, with the highest rank going to the subject with the lowest score, and the lowest rank going to the subject with the highest score. Tied scores result in a DOOR equal to the mean of the tied ranks. The algorithm is exemplified below using a simple scenario with 4 subjects.

Suppose Subject A has an OCO of 1 and 5 days of antibiotic use in the study period (score=1.05), Subject B has an OCO of 1 and 0 days of antibiotic use (score=1.00), Subject C has an OCO of 2 and 0 days of antibiotic use (score=2.00), and Subject D has an OCO of 1 and 5 days of antibiotic use (score=1.05). Because Subject B has the lowest score, Subject B is given DOOR=1 (the highest rank). Because Subject A and Subject D tie for the next lowest score, they both receive the mean of the next 2 available ranks (2 and 3, which has mean 2.5), and so the DOOR for both Subject A and Subject D is 2.5. Finally, Subject C has the highest score and therefore receives the worst available rank, which is DOOR=4.

6.6. Interim Analyses and Data Monitoring

There will be no interim analysis of efficacy or futility. An interim analysis was performed to assess the assumptions used for sample size calculations including rate of adequate clinical improvement, rate of evaluable subjects, and the frequency of enrolled subjects with PCT ≤ 0.25 ng/mL.

Assumptions underlying the original target sample size of 420 subjects were assessed by a planned, interim, blinded analysis after 213 subjects completed or terminated from the study. The original assumptions were that the overall rate of clinical improvement at Visit 3 would be 80% and that there would be no more than 15% unevaluable subjects (i.e. withdraw, fail to complete D5V or didn't meet other inclusion criteria for the according-to-protocol population at Day 5). In this interim analysis, the required sample size needed for 80% power to rule out a 12.5% increase in the clinical improvement rate with antibiotic therapy compared to placebo was computed using the observed overall rate of clinical improvement across both treatment groups and the observed proportion of subjects eligible for an according-to-protocol analysis at D5V. The findings of the interim analysis concluded that 674 subjects needed to be randomized to achieve an ATP-5 sample size of 560 (280 per arm) to achieve 80% power using clinical improvement rate of 57.6% in each group allowing for 16.9% loss in each treatment group. The protocol was updated to reflect the updated sample size.

6.7. Multicenter Studies

This is a multicenter study. Data will be pooled across all clinical sites and analyses will not adjust for potential site effects. However, indicators for site of enrollment will be used in the multiple imputation models.

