## **5.4 Treatment Assignment Procedures**

### **5.4.1 Randomization Procedures**

Per International Council on Harmonisation (ICH) guideline E6: Good Clinical Practice (GCP), screening records will be kept at each participating site to document the reason why an individual was screened, but failed trial entry criteria. The reasons why individuals failed screening will be recorded on screening logs maintained by each site. Once consented and upon entry of demographic data and confirmation of eligibility for this trial, the subject will be enrolled. Only if the PCT is confirmed to be  $\leq 0.25$  ng/mL, will the subject be randomly assigned to 1 of 2 groups (1:1 ratio) to receive either azithromycin or placebo. Subjects with a PCT  $> 0.25$  ng/mL will remain enrolled but will not be randomized to receive study drug.

Enrollment of subjects will be performed online using AdvantageEDC. Lists of randomized treatment assignments will be prepared by statisticians at The Emmes Corporation and included

in The Emmes Corporation's Internet Data Entry System (IDES). IDES will assign each randomized subject a treatment code from the list after the necessary data has been entered into the system. Each site will have a supply of bottles pre-labeled with treatment numbers. Once a participant is assigned a treatment number, the corresponding bottle will be distributed to the participant. An unblinded pharmacist at each site will be provided with a treatment key, which links the treatment code to the actual treatment assignment, which will be kept in a secure place. Subjects will be stratified by site.

Instructions for subject enrollment are included in the Manual of Procedures (MOP). Manual back-up randomization procedures are provided in the MOP for use in the event that the site temporarily loses access to the Internet or the online enrollment system is unavailable.

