3.3.2. Clinical Improvement at D5V

Clinical improvement at D5V is defined as fulfillment of **all** the following criteria.

1. Improvement in at least two symptoms present at enrollment (i.e., cough, sputum production, chest pain, or difficulty breathing) *or* one symptom and at least one vital sign abnormality present at enrollment. For symptoms, at least a one-step improvement (e.g., improvement from moderate to mild cough) will be considered a clinical improvement (Table 1). For vital sign abnormalities,

normalization of the presenting abnormal vital sign will be considered a clinical improvement. Qualifying vital signs and their normal values will include the following:

- temperature (<37.8°C or 100.0°F),
 - pulse (<90 bpm),
 - respiratory rate (≤20 breaths per minute),
2. Absence of deterioration in any qualifying symptom (i.e., cough, sputum production, chest pain, or difficulty breathing); or new vital sign abnormality not present at enrollment. For symptoms, at least a one-step deterioration (e.g. worsening from mild to moderate cough) will be considered clinical deterioration.
 3. Absence of fever in the day preceding or at the D5V (fever is defined as ≥37.8 °C or 100.0 °F, measured anywhere on the body).
 4. No medically attended visit to an ambulatory medical facility (e.g., ED, outpatient clinic, urgent care center) or hospitalization for persistent or worsening LRTI at any time after randomization (persistent or worsening LRTI is defined as receipt of a non-study antibiotic [parenteral or oral] treatment for LRTI or its complication). **Note:** receipt of a non-study antibiotic after study day 5 will not be regarded as satisfying this definition if it is related to a new non-respiratory process that is unrelated to the prior diagnosis of LRTI

Table 1: LRTI-Related Symptoms to Define Clinical Improvement Endpoint

	Mild	Moderate	Severe
Cough*	Occasional coughing (less than hourly)	Frequent coughing (1 or more times an hour and interferes with activity or sleep)	Almost constant coughing (never free of cough or need to cough, makes activity or sleep nearly impossible)
Sputum production*	Noticeable as a problem but does not interfere with activity	Causes a great deal of inconvenience	An almost constant problem
Chest pain	Noticeable only when coughing	Noticeable during deep breaths and when coughing	Almost constant, present even when resting, without cough

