6.4. Covariates and Subgroups

Subjects will be recruited from multiple clinical sites, and randomization will be stratified by site. No subgroup analyses will be performed. Study day of D5V and treatment indicator will be included as covariates in the linear regression model for clinical improvement at D5V. Similarly, study day of D11V and study day of D28V will be included as covariates in the linear regression model for clinical improvement for D11V and D28V, respectively. Covariates to be included in the multiple imputation models are listed in Section 8.4.

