6.5.1. Clinical Improvement at D5V

Clinical improvement at D5V is defined as fulfillment of all the following 1) Improvement in at least two symptoms present at enrollment (i.e., cough, sputum production, chest pain, or difficulty breathing) or one symptom and at least one vital sign abnormality present at enrollment 2) Absence of deterioration in any qualifying symptom (i.e., cough, sputum production, chest pain, or difficulty breathing); or new vital sign abnormality not present at enrollment 3) Absence of fever in the day preceding or at the D5V 4) No medically attended visit to an ambulatory medical facility (e.g., ED, outpatient clinic, urgent care center) or hospitalization for persistent or worsening LRTI at any time after randomization. Persistent or worsening LRTI is defined as receipt of a non-study antibiotic [parenteral or oral] treatment for LRTI or its complication. However, receipt of a non-study antibiotic after study day 5 will not be regarded as satisfying this definition if it is related to a new non-respiratory process that is unrelated to the prior diagnosis of LRTI.

Subjects will be assessed on whether they were enrolled based on at least two qualifying symptoms (cough, sputum production, chest pain, or difficulty breathing) or based on one qualifying symptom and one abnormal vital sign. Severity recorded on the LRTI Symptoms and Fever form (LRT) for Visit 1 will be used as baseline. Vital signs results recorded on the Vital Signs form (VS1) for Visit 1 and Visit 3 will be used to

derive normal or abnormal results for temperature, pulse, and respiratory rate for baseline and D5V, respectively. Symptoms severity for D5V will be obtained from the Solicited Events form (LRS) for the event date corresponding to the Visit 3 date from the Visit Documentation form (VD4). Normal values for the vital signs are:

- temperature ($<37.8^{\circ}\text{C}$ or 100.0°F),
- pulse (<90 bpm),
- respiratory rate (≤ 20 breaths per minute),

6.5.1.1. Improvement in Two Symptoms or One Symptom and One Vital Sign Present at Enrollment at D5V

For symptoms, clinical improvement at D5V will be defined as presence of at least one-step improvement in two qualifying symptoms present at enrollment. For subjects who qualified based on one symptom and one vital sign, normalization of the presenting abnormal vital sign and at least one-step improvement in the symptom will be considered a clinical improvement.

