8.4. Imputation of Missing Data

8.4.1. Multiple Imputation of Missing Values of Clinical Improvement on Day 5, Day 11, and Day 28

Primary and secondary analyses using the ITT population depend on multiple imputation of clinical improvement on D5V, D11V, and D28V. First, a table showing the number and percentage of missing data for clinical improvement on D5V, D11V, and D28V will be presented in Table 20. Regardless of the percent of missingness, multiple imputation will be used for all ITT analyses. Robustness of the multiple imputation

model will be assessed by tipping point analyses. The results of this sensitivity analyses will be provided in [Table 27](#) for D5V, [Table 28](#) for D11V and [Table 29](#) for D28V. In order to use the MI model to adjust for bias caused by missing data, we assume that data is missing at random (MAR).

For missing clinical improvement on D5V, D11V, or D28V, multiple imputations of missing clinical improvement on D5V, D11V, or D28V will be performed independently, and each subject will have their missing clinical improvement imputed independently of other subjects' imputations using a subject-specific imputation model. The pseudocode shown below details how missing data for clinical improvement for D5V (D11V or D28V) will be imputed using m multiply imputed datasets from linear models. The following covariates will be used non-missing for the MI model: treatment group, site indicators, age, gender, study day of D5V (centered at 5), presence of fever on Day 1, and presence of fever on D5V. The number of imputed, m , datasets will be chosen based on the average percent of missing data. Default value will be $m=20$ since sample size calculation assumed close to 20% drop-out rate.

As a first step to multiple imputation, an ordered list of variables to include in the subject-specific imputation model is constructed. Ordering is specified so that exact imputation results from final data are prespecified may be replicated in SAS (using seeds described below). The complete ordered list of variables for the imputation models for clinical improvement is below:

- Treatment Group (azithromycin is reference)
- Indicator of subject enrolled at the site with the second most number of subjects enrolled (binary indicator)
- Indicator of subject enrolled at the site with the third most number of subjects enrolled (binary indicator)

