- Indicator of subject enrolled at the site with the fourth most number of subjects enrolled (binary indicator)
- Indicator of subject enrolled at the site with the least number of subjects enrolled (binary indicator)
 - Note: the site with the most number of subjects enrolled is reference for site. Language is written to allow for an arbitrary number of sites. In the event of a number of ties for the number of subjects enrolled, tied sites will be ordered in ascending alphanumeric order in the list of model variables.
- Age at enrollment
- Gender (Male is the reference)
- Study day of D5V (centered at 5)
- Presence of fever on Day 1 as recorded on the Assessment of LRTI Symptoms and Fever (LRT) form
- Presence of fever in the day preceding or at the D5V as recorded on Solicited Events or vital signs form

The actual list of MI model variables for each subject-specific imputation model will follow the ordering above but omit variables with missing values. The below pseudo-code / SAS code outlines the creation of 20 multiple imputation datasets. Note that the seeds used in the actual analysis must follow the specification given in the pseudo-code and subjects must be processed in the order described in the pseudo-code. The pseudo-code is for D5V, but the general logic is also applicable to D11V and D28V.

*Outcome variables: clinimprove_D5V

DEFINE i=index variable for subjects having clinical improvement imputed.

Subjects requiring imputation are sorted in ascending order by PATID.

DEFINE N=number of subjects requiring imputation

DEFINE g&i=analysis dataset containing predictors and clinical improvement for

ATP-5 subjects as well as subject i (only one subject not in ATP-5 included). Note that ATP-5 subjects that are missing a value for one or more variables in the subject-specific imputation model are excluded.

DEFINE imp_g&i = g&i, with 20 imputed values for the missing clinical improvement

added by PROC MI

DEFINE &&modelVars_&i = list of observed variables in subject i (treatment group, site1, site2, site3, site4, age, gender, cstday5, fever), to be used for imputation of clinical improvement

Step 1: Imputation model: This model will generate 20 datasets with each dataset containing original complete data along with imputed values for subjects with missing endpoint.

```
%do i=1 %to &N;
```

```
PROC MI data= g&i out= imp_g&i seed= 22131&i NIMPUTE=20 noprint;
```

```
  Var &&modelVars_&i clinimprove_D5V;
```

```

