  monotone regression(clinimprove_D5V) = &&modelVars_&i;
```

```
run;
```

```
%end;
```

imp_g&i will be subset to contain only rows for the subjects with imputed clinical improvement and merged together and with ATP-5 data to create the twenty complete multiply imputed datasets

Step 2: Analysis model: This model will fit regression models to the 20 complete datasets to obtain parameter estimates for treatment success, clinical cure, microbiological success.

```
proc reg data= imp_g outest= out_clinimp_D5V covout noprint;
```

```
model clinimprove_D5V= trt cstday5/clb alpha=0.05;
```

```
by _imputation_;
```

```
run;
```

Step 3: Combine estimates from models in step 2 to obtain overall estimates summarized over 20 imputed datasets;

```
proc mianalyze data= out_clinimp
```

```
  _D5 alpha = 0.05;
```

```
modeleffects intercept trt cstday5;
```

```
ods output ParameterEstimates=parms_trts;
```

```
run;
```

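### The primary ITT model leaves out site (the stratification factor) and graded Visit 1 symptom severity, so its interval may be wider than necessary; an ITT risk difference without visit day is also not planned

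*SAP*

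**What the plan says.** **Stratification.** Protocol 5.4.1: "Subjects will be stratified by site". SAP 6.4 agrees: "Subjects will be recruited from multiple clinical sites, and randomization will be stratified by site".

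**Analysis model.** SAP 6.7: "Data will be pooled across all clinical sites and analyses will not adjust for potential site effects". Step 2 of SAP 8.1.1 regresses the improvement indicator on treatment and centred D5V day, and the code in SAP 8.4.1 matches: "model clinimprove_D5V= trt cstday5/clb alpha=0.05". Protocol 11.4.1 also names visit day as a covariate.

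**Imputation model.** SAP 8.4.1 lists "treatment group, site indicators, age, gender, study day of D5V (centered at 5), presence of fever on Day 1", plus fever at D5V. Site is therefore used for imputation only. Graded symptoms are not listed.

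**Baseline severity.** SAP 6.5.1: "Severity recorded on the LRTI Symptoms and Fever form (LRT) for Visit 1 will be used as baseline". The first endpoint criterion in SAP 3.3.2 requires "Improvement in at least two symptoms present at enrollment (i.e., cough, sputum production, chest pain, or difficulty breathing", or one symptom together with one abnormal vital sign.

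**Visit day.** D5V may fall on Days 5 to 8, and a missed or out-of-window visit is assigned Day 5 (SAP 3.3.1). The footnote to Table 21 says the reported rates refer to a Day 5 visit. The ITT tipping-point analysis (SAP 8.2.4) adjusts for visit day too. Miettinen-Nurminen intervals without visit day are planned for the ATP populations only (SAP 8.2.1 and 8.2.3).

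**The concern.** SAP 8.1.1 rests the non-inferiority conclusion on the primary analysis alone, so one lower bound compared with -12.5 points decides the trial. Site and Visit 1 severity are fixed before treatment. Adjusting for them cannot introduce post-randomization bias, and it removes outcome variance if they predict improvement.

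There is a structural reason to expect some link for severity. On the symptom route, a subject who enters with two symptoms must improve in both, while one who enters with four needs any two. The rule shows that baseline burden and outcome are connected. It does not show how strongly, or with what sign.

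Visit day is a separate and lesser matter. It is measured after randomization, and every planned ITT risk difference for clinical improvement conditions on it. A reader cannot see from a formal ITT interval whether that conditioning moved the bound.

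**Working it through.** **Inputs from the documents.** Margin 12.5 points; two-sided 95% interval; 57.6% improvement in each arm; 560 evaluable (280 per arm); 16.9% loss; 674 randomized (337 per arm) (Protocol 11.2, SAP 5). **Not in the documents:** any R-squared for site or severity. I assume 2-10%.

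**The plan's own figures.** 560/(1 - 0.169) = 673.9, so 674 reproduces. The 560 does not: with the usual continuity correction (interval widened by 1/n), 262 per arm gives 80% power, and 280 gives 82.8%. The plan's number is conservative, and this does not affect the present point. The figures below omit the correction because the regression interval has none.

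**Planned model.** SE = sqrt(2 x 0.576 x 0.424/n).
- n = 337: SE = 0.03807; half-width 1.96 x SE = 7.46 points; power = Phi(0.125/0.03807 - 1.96) = Phi(1.323) = 90.7%.
- n = 280: SE = 0.04177; half-width 8.19 points; power 84.9%.

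337 per arm is an upper bound on the information, because some ITT outcomes will be imputed.

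**With baseline covariates.** The SE is multiplied by sqrt(1 - R-squared).

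| Assumed R-squared | Half-width, n = 337 | Power, n = 337 | Half-width, n = 280 | Power, n = 280 |
|---|---|---|---|---|
| 0 | 7.46 | 90.7% | 8.19 | 84.9% |
| 2% | 7.39 | 91.3% | 8.10 | 85.6% |
| 5% | 7.27 | 92.1% | 7.98 | 86.7% |
| 10% | 7.08 | 93.3% | 7.77 | 88.4% |

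At 337 per arm the planned interval is thus 1.0%, 2.6% or 5.4% wider than the adjusted one.

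**If neither covariate is prognostic.** The planned model leaves 674 - 3 = 671 residual degrees of freedom. Protocol 5 and the SAP site shells each name six sites, but not the same six; together they name seven. Site indicators plus one severity term therefore add q = 6 or 7 terms. Multiplying the variance by 671/(671 - q) gives power 90.47% or 90.43% against 90.71%, a loss of 0.24 to 0.28 points.

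**Simulation checks.** With 674 subjects, six sites and 1:1 allocation within site (2,000 runs per setting), the ratio of planned to adjusted SE was 1.009, 1.024 and 1.049 at observed R-squared of 2.7%, 5.6% and 10.1%. With no true covariate effect it was 0.999. Coverage of the planned model was 94.4-94.7%. In 10,000 simulated trials at the margin, with between-site SD of 0/5/10/15 points, one-sided type I error was 0.025/0.022/0.023/0.019 without site and 0.025/0.023/0.026/0.024 with site (Monte Carlo SE about 0.0016).

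**Visit day.** With complete data, the unadjusted difference equals the adjusted difference plus the slope per day times the between-arm difference in mean visit day. Both factors are unknown. If the slope were 3-8 points per day and the means differed by 0.1-0.3 day (both assumed), the two estimates would differ by 3 x 0.1 = 0.3 to 8 x 0.3 = 2.4 points, in either direction.

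**The case against.** The covariate set is a stated choice on which protocol and SAP agree. Site already enters the imputation. Coverage is near nominal, and power exceeds the 80% target at both 280 and 337 per arm. The gain depends on an R-squared that nobody has reported, and a sum of four grades is a construct the documents do not use. The fix re-specifies the primary estimator at a late stage: the screening-date shell (Table 10) ends in March 2020, and SAP 6.3.2 describes the deviation review as done.

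Most of this stands, and it limits the point to lost precision. It does not remove it. Using site for imputation does not take between-site variance out of Step 2. Exceeding 80% power under planning assumptions is no reason to leave precision unused when one bound decides the trial.

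On visit day, the covariate has a purpose, since it targets the difference at Day 5. Under equal arms, simulated adjusted and unadjusted estimates agreed within 0.02 points. A crude observed-case comparison can also be built from Table 49, because ordinal outcomes 1-4 mean improvement, apart from subjects whose ordinal outcome is missing. ITT also has DOOR analyses and longitudinal summaries without a visit-day term (Tables 37, 46 and 52-55). None of these is a formal risk difference for clinical improvement.

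A reader might infer that ignoring the stratification factor invalidates the test. The documents do not support that: pooling over a stratifier tends to make the interval conservative, and the simulated error rates were at or below nominal.

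**Conclusion.** The plan is valid as written, but it may forgo a modest gain in precision. Under an assumed R-squared of 2-10% at 337 per arm, the half-width would fall by 0.07 to 0.38 points and power would rise by about 0.6 to 2.6 points. With no prognostic value, the covariates would cost 0.2-0.3 points. These figures assume complete data and the plan's 57.6% rate.

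Two stronger readings should be avoided. The first is that the interval is wider than it need be as a matter of fact; without an R-squared this stays conditional. The second is that visit-day adjustment biases the primary result. It is measured after randomization and could matter, but it serves the stated Day 5 target, and the unadjusted estimate can be off as well. The extra row is a transparency check, and it cannot settle which estimate is right.

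**What to change.** Before unblinding:

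1. In SAP 6.4, 6.7, 8.1.1 Step 2 and 8.2.1-8.2.3, with matching wording in Protocol 11.4.1, add site indicators coded as in SAP 8.4.1, where the note already says "Language is written to allow for an arbitrary number of sites". Prespecify a rule for pooling very small sites.
2. In the same places add one prespecified baseline severity term, for example the sum of the four Visit 1 grades (none 0 to severe 3). Centre it and the site indicators so that the Step 3 expressions still give the arm rates.
3. Add the severity term to the imputation list in SAP 8.4.1.
4. Supportive: keep D5V day in the primary model. Beside Table 21 add one ITT multiple-imputation risk difference with D5V day left out of both the imputation list and Step 2. Tabulate D5V day by arm, with the number of subjects assigned Day 5, and state that neither estimate is the reference for the other.

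The cost is a few lines of text and code, a pooling rule, one table row, one small table and a protocol wording change. The main cost is that it changes the primary estimator, so the change must be dated and documented as made blind. If that is no longer possible, keep the planned model as primary and report the adjusted model as supportive.
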